6.1. Recruiting Participants with Differing Mental Capacity

Following evaluation of capacity (as outlined in the Mental Capacity Act (MCA) 2005), thermally injured participants enrolled in this study will fall into the following groups:

6.1.1. Adult Participants Determined to Have Mental Capacity at Study Entry and Throughout the HESTIA Study

Those participants who present with capacity and meet study entry criteria will be provided with a Participant Information Leaflet (PIL) outlining the study. If the participant agrees to consent to the HESTIA study following a discussion with the research team, they will be asked to sign a consent form.

Given the short (24 hour) window for recruitment, those patients who are acutely unwell will initially be presented with an abbreviated PIL. Once stable, this will be followed by the standard information leaflet and re-confirmation of consent.

6.1.2. Adult Participants Lacking Mental Capacity for the Duration of the HESTIA Study

It is anticipated that some subjects who meet eligibility criteria for this study will not be able to give informed consent due to their medical condition or its management (e.g. sedation, opioid analgesia, intubation). In such cases, participants may be enrolled in the study in accordance with Section 30- Section 34 of the MCA 2005. The decision to enroll the participant will be discussed with a personal or nominated consultee (as defined in Section 12.3.2). This decision may or may not be witnessed by an independent witness according to the decision of the principal investigator.

6.1.3. Adult Participants Lacking Mental Capacity (either at Study Entry or During the Study) Who Later Regain Capacity and Are Required to Provide Informed Consent

As soon as is practically possible following a participant regaining capacity, participants will be asked to provide informed consent to remain in the study. If they decline, then they will be withdrawn from the study as soon as it is safe to do so (likely immediately given the design of this study). Samples and data collected prior to study withdrawal may be retained. The participant will be asked about this at the point of study withdrawal.

6.1.4. Adult Participants with Mental Capacity to Provide Consent at Study Entry Who are Later Deemed No Longer to have Mental Capacity

The decision for the participant to remain in the study will be discussed with a personal or nominated consultee and recorded. If the participant subsequently regains capacity again, they will be asked to re-consent to study participation.

When considering enrolment of participants who lack the mental capacity to consent, the following should be noted:

- Section 3.2.1 of the SIFTI-2 protocol describes the consent process for that study in detail and should be read in conjunction with this protocol.
- A Study Information Leaflet will be provided to the personal or nominated consultee outlining the HESTIA trial before being asked to sign a form supporting the participant's enrolment in the study.
- The investigator and/or the site's IEC/IRB have responsibility for acting in accordance with the MCA 2005 in the matter of assessing who has the capacity to consent and who qualifies as a personal or nominated consultee of a potential subject. The investigator will also decide if an independent witness is required.
- Further information regarding the assessment of mental capacity and the appointing of personal or nominated consultee is given in [Appendix 3](#) (Section [12.3.2](#) and Section [12.3.3](#)).
- If a patient loses mental capacity subsequent to their consent and enrolment to the HESTIA study, samples and data collected prior to loss of capacity will be retained even if approval of continued study participation by a personal or nominated consultee is declined.

6.2. Inclusion Criteria for Healthy Participants (Group 1)

1. Males or Females must be ≥ 18 years of age at the time of signing informed consent.
2. Participants who are healthy as determined by the investigator following medical evaluation including medical history, physical examination, and laboratory tests (these are listed in [Appendix 2](#)).
3. Female participants:
A female participant is eligible to participate if she is not pregnant (negative pregnancy testing at screening or Day 1 as needed) and not breastfeeding.
4. Capable of giving signed informed consent as described in [Appendix 3](#) which includes compliance with the requirements and restrictions listed in the informed consent form (ICF) and in this protocol.

6.3. Inclusion Criteria for Thermal Injury Participants (Group 2)

Thermal injury participants are eligible to be included in the study only if all of the following criteria apply:

6.3.1. Age

1. Participant must be ≥ 18 years of age.

6.3.2. Type of Participant and Disease Characteristics

2. Participants who have sustained a burn (thermal injury) with a TBSA $\geq 15\%$.

6.3.3. Other Inclusions

3. Admission to the burn centre (study site) ≤ 24 hours of injury.

4. Able to take enteral fluids either orally or via a nasogastric tube (depends on facial burn damage).

6.3.4. Gender

5. Male and female.

a. Female participants:

A female participant is eligible to participate if she is not pregnant (negative pregnancy testing at study entry) and not breastfeeding.

6.4. Exclusion Criteria for Healthy Participants (Group 1)

1. Healthy participants are excluded from this study if they are receiving anti-coagulation therapy.
2. Pregnancy or breastfeeding.
3. A body mass index $>34\text{kg/m}^2$
4. An active history of alcohol dependency
5. History of sensitivity to any of the STM, or components thereof or a history of drug or other allergy that, in the opinion of the Investigator and/or GSK Medical Monitor, contraindicates their participation.
6. A positive pre-study Hepatitis B surface antigen or positive Hepatitis C antibody and confirmatory Hepatitis C PCR result within 3 months of screening.
7. A positive pre-study urine drug/alcohol screen.
8. A positive test for HIV antibody.
9. Participants unable to swallow large capsules (the capsules will be shown to participants at screening).
10. Galactosaemia or severe lactose intolerance.
11. Use of an antibiotic 2 weeks prior to study start (i.e. administration of the STM).
12. Gastroenteritis in the 2 weeks prior to study start (i.e. administration of the STM).

6.5. Exclusion Criteria for Thermal Injury Participants (Group 2)

Thermal injury participants are excluded from the study if any of the following criteria apply:

Medical Conditions

1. Chemical or electrical burn.
2. Multiple traumatic injuries with an Injury Severity Score (ISS) ≥ 16 (note: excludes burn in score system).

Prior/Concomitant Therapy

3. Patient received substantial undocumented management prior to arrival at the study site (burn centre) e.g. from paramedics or in a local accident and emergency department.
4. Systemic corticosteroid use.
5. Intravenous (IV) mannitol use.

Prior/Concurrent Conditions

6. Human immunodeficiency virus (HIV) infection.
7. Viral Hepatitis B or C infection.
8. Gastrointestinal disease (e.g. inflammatory bowel disease) which may affect intestinal permeability.
9. Previous bowel resection (e.g. hemicolectomy, small bowel resection)
10. Galatosaemia or severe lactose intolerance.
11. Bowel obstruction.
12. Renal dysfunction requiring renal replacement therapy (i.e. end-stage renal failure prior to thermal injury).
13. Active autoimmune disease and receiving immunomodulatory therapy e.g. rheumatoid arthritis anti-TNF.
14. Active chemotherapy for cancers or immunoremittive therapies (prednisolone, adalimumab) within 60 days of thermal injury.
15. Premorbid conditions of malignancy currently under treatment.
16. Previous bilateral lower extremity amputation.

NOTE: Due to the rapid recruitment period (within 24 hours of admission) for thermally injured participants, HIV and viral Hepatitis test results may not be available at the time of enrolment. In the event these tests return positive, the participant will be informed of the result(s) and withdrawn from the study (see Section 8.2.1). In the event that the participant has been recruited who lacked mental capacity to consent, the reason for their withdrawal (the positive HIV and/or viral Hepatitis test results) must not be shared with a personal consultee. According to UK law and the guidance of the British HIV association, if the participant's physician believes there is an overriding public interest to disclose the participant's results to a personal consultee who is a current or former sexual partner, then the result(s) may be disclosed without the participant's consent. This must be as a last resort. If the participant regains capacity, he/she will be informed of the positive test result(s).

Diagnostic assessments

17. Decision not to treat the patient due to futility.

6.6. Lifestyle Restrictions

6.6.1. Meals and Dietary Restrictions

- Participants will be fasted (or feed stopped) for **3 hours** prior to STM administration and for **3-5 hours** afterwards. For thermally injured participants these fasts should be aligned with those required for routine clinical care (feed holds, before surgical interventions) where possible.
- Refrain from consumption of the following for **24 hours** before and after the administration of STM:
 - Foods/drinks/medicines and other products which contain sucralose, lactulose or mannitol as artificial sweeteners.

N.B. If cannot be avoided, then clear documentation of its administration is required and the current test to stop. If urine samples have been collected PRIOR to administration of the drug, then these can still be sent for analysis

6.6.2. Alcohol/Exercise/Aspirin (Healthy Participants only)

Alcohol, aspirin and vigorous exercise [Sequeira, 2014] are all known to cause transient increases in intestinal permeability. Healthy participants will therefore be requested to avoid alcohol, aspirin and physical exercise for **48 hours** before taking the STM and for the 24-hour urine collection period.

6.7. Screen Failures

There will be no screening period for thermal injury participants. Screening will be up to 28 days before Day 1 for healthy participants.

Screen failures are defined as participants who consent to participate in the clinical study but are not subsequently entered in the study. A minimal set of screen failure information is required to ensure transparent reporting of screen failure participants to meet the Consolidated Standards of Reporting Trials (CONSORT) publishing requirements and to respond to queries from regulatory authorities. Minimal information includes demography, screen failure details, eligibility criteria, and any serious adverse events (SAEs).

Individuals who do not meet the criteria for participation in this study (screen failure) may be rescreened. Rescreened participants should be assigned a new participant number.

7. NON-INVESTIGATIONAL MEDICINAL PRODUCT (NIMP)

A study treatment is defined as any investigational treatment(s), marketed product(s), placebo, or medical device(s) intended to be administered to a study participant according to the study protocol. According to this definition, no GSK study treatment will be employed in this study.

The STM (comprising lactulose, mannitol and sucralose) will be intermittently administered enterally as a study challenge agent to measure permeability at different points along the GI tract. Lactulose and Mannitol assess small intestine permeability and sucralose to assess colonic permeability.

It is important to note that the administration of the STM is not therapeutic (lactulose and mannitol can be used as laxatives, however the amount in the STM is sub-therapeutic) and as such should be regarded as a non-investigational medicinal product (NIMP) [[Guidance Documents Applying Investigational Medicinal Products \(NIMPS\)](#), 2011].

7.1. STM Administered

Study Treatment Name	Lactulose (4- α -D-galactopyranosyl-D-fructofuranose)	Mannitol (D-mannitol) GRAS listed	Sucralose (1,6-Dichloro-1,6-dideoxy- β -D-fructofuranosyl-4-chloro-4-deoxy- α -D-galactopyranoside)
Dosage formulation	oral solution	oral solution	Capsules (powder)
Unit dose strength(s) Adults	5g	2g	2g (3 capsules to deliver total 2g sucralose)
Route of Administration	Oral / nasogastric / nasojejunal	Oral / nasogastric / nasojejunal	Oral / nasogastric / nasojejunal (capsules to be opened and contents added to lactulose and mannitol for tube administration)
Preparation and Dosing instructions	
For oral administration, the lactulose and mannitol will be prepared as a 100ml drink to be taken with 3 sucralose capsules.
 
For feeding tube administration, lactulose/mannitol/sucralose will be prepared as a 50ml solution and given via a feeding tube followed by an immediate 50ml drinking water flush
 
Preparation refer to Study Reference Manual together with SoA tables (Section 2)
		
Packaging and Labelling	Lactulose and Mannitol will be supplied pre-mixed in an amber bottle (or equivalent) for single use. Each container will be labelled as required per country requirement.		Sucralose will be provided as capsules in a storage container. Each container will be labelled as required per country requirement.
Manufacturer	Tayside Pharmaceuticals, UK		
Storage	Lactulose/Mannitol formulation should be stored under refrigerated conditions. The sucralose capsules should be stored at room temperature in a dry environment away from direct sunlight.		
Shelf-life	Lactulose/Mannitol pre-mix formulation and sucralose capsules supplied by Tayside Pharmaceuticals will have at least 3 month shelf-life when stored at the correct storage conditions.		

The preparation of the STM for oral use and nasogastric/nasojunal tube administration can be found in the Study Reference Manual.

7.2. Dose Modification

Dose modification will not be required. Unit dose is described in Section 7.1.

7.3. Method of STM Administration: Treatment Assignment

There is no element of randomisation in the study and all study participants will receive the STM according to the relevant SoA. The method of administration can be found in the Study Reference Manual.

7.4. Blinding

No GSK study treatment will be employed in this study. All participants will receive the same STM and all thermal injury participants will perform the same study procedures.

7.5. Preparation/Handling/Storage/Accountability

1. The investigator or designee must confirm appropriate temperature conditions have been maintained during transit for all STM received and any discrepancies are reported and resolved before use of the STM.
2. Only participants enrolled in the study may receive STM and only authorized site staff may supply or administer STM unless adequate training is provided such as in the case of healthy participants. All STM must be stored in a secure, temperature controlled, and monitored (manual or automated) area in accordance with the labeled storage conditions with access limited to the investigator and authorized site staff.
3. The investigator, institution, or the head of the medical institution (where applicable) is responsible for STM accountability, reconciliation, and record maintenance, as needed.
4. Further guidance and information for the final disposition of unused STM are provided in the Study Reference Manual.
5. Under normal conditions of handling and administration, STM is not expected to pose significant safety risks to site staff.

7.6. STM Compliance

- When participants undergo intestinal permeability testing at the site, they will receive STM directly from the investigator or designee, under medical supervision. The date and time of each dose administered in the clinic will be recorded in the source documents. The dose of STM and study participant identification will be confirmed at the time of dosing by a member of the study site staff other than the person administering the STM.

- If healthy participants need to prepare and administer the STM off-site such as at home, STM training will be provided and a record maintained by the investigator or designee.

7.7. Concomitant Therapy

- Refrain from consumption of the following for **24 hours** before and after the administration of STM:
 - Lactulose or mannitol-containing laxatives. Study sites will be asked to use movicol (polyethylene glycol) in place of lactulose.
 - Medicines with mannitol as an excipient (chlorthiazide sodium, some albumin preparations, some laxatives, tablets as a bulking agent).
 - Products containing sucralose.
- For healthy participants only, refrain from consumption of aspirin for **48 hours** before taking the STM and for the 24-hour urine collection period see Section [6.6.2](#).
- For healthy participants only, antibiotic use 2 weeks prior to STM administration and during the study is not permitted.
- Sennoside laxatives should be avoided. These can cause gastrointestinal irritation and may contribute to raised intestinal permeability.
- Additional Glutamine supplementation in excess of that delivered with a standard feeding protocol should be avoided during the first 28 days of study participation. If supplementation is given inadvertently, then the patient will remain in the study, but the total dose and duration of additional glutamine supplementation must be recorded in the CRF.
- Thermal injury participants that receive Intravenous (IV) mannitol for renal failure or raised intracranial pressure (testing to be delayed until 12 hours after last administration).

7.8. Treatment after the End of the Study

There will be no ongoing STM administration following the end of this study.

8. DISCONTINUATION CRITERIA

8.1. Discontinuation of STM administration

Discontinuation of STM administration can be considered by the investigator in the event that an adverse event to the STM is observed. Withdrawal of further STM administration does not require withdrawal from the study.

8.2. Withdrawal from the Study

- A participant may withdraw from the study at any time at his/her own request, or may be withdrawn at any time at the discretion of the investigator for safety, behavioural, compliance or administrative reasons.
- If the participant withdraws consent for disclosure of future information, the sponsor may retain and continue to use any data collected before such a withdrawal of consent.
- If a participant withdraws from the study, he/she may request destruction of any samples taken and not tested, and the investigator must document this in the site study records.

8.2.1. Other Withdrawal Criteria

- A participant will be withdrawn from the study following positive (and confirmed) HIV test at screening; Serologic evidence of active Hepatitis B (HB) infection based on the results of testing for HBsAg, and anti-HBc or a positive test for Hepatitis C antibody confirmed by Hepatitis C RNA or antigen testing. If HCV RNA is not available, then the positive test for Hepatitis C antibody alone would be exclusionary. Results must be discussed with the medical monitor to withdraw the participant from the study and commence therapy according to local practice.
- Healthy participants that are treated with antibiotics during the duration of the study.
- Participants that experience signs and symptoms of gastro-intestinal infections during the duration of the study.
- Withdrawals related to mental capacity as described in Section 6 and [Appendix 3](#).
- Participants that received haemodialysis during the first 48 hours of the study (i.e. during the first measurement of intestinal permeability) will be excluded from the evaluable population and a replacement will be recruited.
- Participants that received haemodialysis during later time points will not be excluded, but consideration will be given to recruiting an additional participant if 3 or more intestinal permeability measurements occur concurrently with haemodialysis.

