2. SCHEDULE OF ACTIVITIES (SOA)

2.1. Healthy Participants (Group 1)

Procedure	Screening	Treatment Period [Out patient days] (\pm 1 day)			Notes
		D1	D8	D15	
Review of inclusion/exclusion criteria and informed consent	X				
Demography	X				
Medical history (includes substance and alcohol usage at screening) and Medication history	X				
Substance testing (urine)	X				Substances: [Recreational Drugs and Alcohol]
HIV, Hepatitis B and C screening	X				If test otherwise performed within 3 months prior to study entry, testing is not required
Laboratory assessments	X				
Pregnancy test (WOCBP only) (urine)	X	(X)			Only performed again on Day 1 if patient at risk of pregnancy at or since screening

Procedure	Screening	Treatment Period [Out patient days] (± 1 day)			Notes
		D1	D8	D15	
Blood sampling for biomarkers		X			20ml of blood will be sampled in a single draw on one day, preferably Day 1
Stool sample collection		X			Participants will be given a collection container at screening to bring with them on Day 1.
Brief physical examination including measurements of height and weight Vital Signs (systolic and diastolic blood pressure and heart rate)	X	X	X	X	BMI calculated from height and weight at screening only Examinations should be conducted the day after intestinal permeability measurement.
Medical review (assessment of health status)		X	X	X	Monitor for signs and symptoms of gastro-intestinal infections and other emergent issues
STM Training	X				Refresher training may be provided as needed
Intestinal permeability measurement: STM administration followed by a 24-hour urine collection		X	X	X	Please refer to SRM for full information Intestinal permeability measurement to be performed at home the day before the study visit.

Procedure	Screening	Treatment Period [Out patient days] (± 1 day)			Notes
		D1	D8	D15	
AE/SAE and Concomitant medication reviews	(X)	←=====→			Day 1 will include concomitant medication review only

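### The gastro-intestinal infection criterion in Protocol 8.2.1 is not limited to healthy participants; applied as written, it would withdraw burn participants and end their L/M follow-up

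*Protocol*

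**What the plan says.** Protocol 8.2.1 (Other Withdrawal Criteria) is a list in which some bullets name a group and others do not. One is restricted to Group 1: "Healthy participants that are treated with antibiotics during the duration of the study". The next is not: "Participants that experience signs and symptoms of gastro-intestinal infections during the duration of the study". That second bullet has no verb, so its effect comes from the section heading. Two further bullets, also without a group, deal with haemodialysis. If it occurs in the first 48 hours, the participant leaves the evaluable population and is replaced. For later dialysis the rule is "Participants that received haemodialysis during later time points will not be excluded".

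Elsewhere, the healthy-participant schedule (2.1) attaches this note to the medical review on Days 1, 8 and 15: "Monitor for signs and symptoms of gastro-intestinal infections and other emergent issues". The TI schedule (2.2) has no such item. Among the TI entry exclusions (6.5), the nearest is criterion 8: "Gastrointestinal disease (e.g. inflammatory bowel disease) which may affect intestinal permeability". Section 9 rules out waivers and exemptions.

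**The concern.** A site following the text has no stated basis for sparing a TI participant who develops a gut infection. Appendix 4 Table 3 puts infective diarrhoea and C. difficile infection among the complications that can be regarded as part of severe burn illness, so such events are foreseeable in Group 2.

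Withdrawal would end that person's later HESTIA measurements: L/M ratio, sucralose and stool. L/M over time is co-primary objective 2, and 5.4.2 relies on the Day 28 and 6-month tests to show whether permeability has returned to normal. The study's central hypothesis links burns, barrier damage and bacterial translocation. Dropout triggered by a gut infection could therefore be related to the quantity being measured. Protocol 5.3 itself accepts that later missing data may be related to outcome in either direction.

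**Working it through.** The plan gives no figure on this point. The check is a comparison of sections, followed by a count of scheduled tests.

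**1. Which group was meant?**

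Pointing to Group 1:
- The antibiotic and infection bullets in 8.2.1 parallel healthy-only exclusions 11 (antibiotic use) and 12 (gastroenteritis) in 6.4. Section 6.5 has no gastroenteritis exclusion for TI participants, and its criterion 8 applies only at entry.
- The matching symptom check appears only in the Group 1 schedule.
- The table in 9.4 marks assessment of health status as not required for TI participants.

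Pointing to both groups:
- The adjacent bullet names healthy participants and this one does not.
- Other bullets in the list without a group restriction reach TI participants: the note in 6.5 refers to 8.2.1 for positive HIV or hepatitis tests, and the haemodialysis bullets plainly concern burn patients.

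Group 1 is the better inference, but it remains an inference.

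**2. How are other in-study disturbances of the test handled in TI participants?**

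| Disturbance | Section | Consequence |
|---|---|---|
| IV mannitol | 7.7 | Test delayed until 12 hours after the last dose |
| Unavoidable intake of a test sugar | 6.6.1 | Current test stops; earlier urine still usable |
| Extra glutamine | 7.7 | Participant stays; dose and duration recorded |
| Senna | 3.3.1, 7.7 | Use documented, although it may raise permeability |
| Later haemodialysis | 8.2.1 | Not excluded; an extra recruit is considered if 3 or more tests are affected |
| Haemodialysis in first 48 hours | 8.2.1 | Excluded from the evaluable population and replaced |

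Five of the six keep the participant. The sixth is tied to the first measurement. That measurement is the endpoint for co-primary objective 1 and the denominator of the change model in Protocol 10.6, and under SAP 4.2 and 4.2.1 a missing Day 1 value makes every change from baseline missing. A gut infection after a valid Day 1 test does none of this. Section 8.1 takes the same approach for adverse events to the sugars: "Withdrawal of further STM administration does not require withdrawal from the study".

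**3. What would be lost?**

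Input: the TI schedule in 2.2. Maximum tests = 7 alternate-day + Day 28 + 6 months = 9. Tests lost = tests scheduled after the withdrawal day. The event days are assumptions chosen to show the range, with withdrawal on the same day.

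| Event day | Alternate-day tests lost | Convalescent tests lost | Total lost |
|---|---|---|---|
| 4 | 5 (D5, 7, 9, 11, 13) | 2 | 7 of 9 |
| 8 | 3 (D9, 11, 13) | 2 | 5 of 9 |
| 14 | 0 | 2 | 2 of 9 |
| Between Day 28 and 6 months | 0 | 1 | 1 of 9 |

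The even-day schedule gives the same totals. With discharge on Day 8 and no re-attendance, 4 + 2 = 6 tests apply, and events on Days 4, 8 and 14 lose 4, 2 and 2 of 6. Because the study stopped before any participant reached Day 28 (SAP 1.3), only the seven alternate-day tests could have been affected in practice: 5, 3 and 0 of 7 for the same three days.

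**4. Do existing provisions recover the loss?**

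Data up to withdrawal are listed and summarised (SAP 10.6.1). Protocol 5.3 considers early withdrawals for analysis and plans missing-data sensitivity analyses. Replacement is at the sponsor's discretion (5.2). None of these supplies the missing measurements, and SAP 4.1 imputes nothing across visits.

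**The case against.** The strongest reply is that the wording may be deliberate. Section 7.7 restricts several items to healthy participants, so the authors knew how to limit a rule. Amendment 1 revised 8.2.1 and left this bullet alone, and it reads the same in all three protocol versions. A gut infection can raise permeability for reasons other than the burn, so removing such participants is a defensible choice. If Group 1 was meant instead, the TI consequences do not arise and only a missing adjective remains.

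Much of this stands. Intent is unsettled, and the consequence follows only from the literal text. It does not rescue the rule for TI participants, however. Keeping them and flagging the affected tests lets the analyst exclude those values later, whereas withdrawal removes the choice.

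Two stronger readings should be resisted. A reader might infer that 8.2.1 contradicts Table 3. It does not: Table 3 governs adverse-event reporting and says nothing on whether a participant or a test should be kept. Renal replacement therapy is also in Table 3, yet early haemodialysis leads to removal. A reader might also infer that the protocol otherwise never removes a TI participant for a disturbed test; the early haemodialysis rule shows that it does.

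The consequence should not be stretched to all outcomes. Wound parameters are also collected in SIFTI-2 (9.5.2), and the criterion does not require leaving that study.

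**Conclusion.** The point holds as a drafting defect with a real but conditional consequence. The bullet covers both groups as written, context suggests Group 1, and literal application would create avoidable missing L/M data in TI participants that may be related to outcome. Severity is minor.

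The size rests on two unknowns that the documents do not supply: how often TI participants develop gut infections, and which way the resulting bias would run. The test counts show what one withdrawal would cost on assumed days; they are not estimates of missingness.

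It would be wrong to infer that the reported results were biased by this rule. SAP 1.1 gives 3 TI participants, none reached Day 28, and the final analysis is descriptive, so the effect on the terminated study is negligible. The protocol and SAP do not report participant-level events, so they neither show nor rule out that a TI participant was affected.

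**What to change.** Begin the bullet with 'Healthy participants'. For TI participants, state that follow-up continues and that a sugar test may be delayed or skipped during active gastro-intestinal infection. Section 7.7 gives the precedent with IV mannitol, and the timing note under the schedule in 2.2 already allows such changes. In the SAP, flag L/M values concurrent with infection in Listing 24 and Figures 2.2 and 2.3, where an event date is available from the disease-related events (SAP 7.1, Listing 17) or from SIFTI-2 records.

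The cost is a short amendment, needing ethics approval under 12.3.1, and a flag in existing displays. There are two limits. Some TI values will be measured during infection or delayed by it. The flag will also be incomplete, because TI participants have no scheduled symptom review and Appendix 4 sends events unrelated to HESTIA procedures to the SIFTI-2 record. As the study has ended, the amendment matters mainly if the protocol is reused; the flag can still be applied to the final report.
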